1.0 Introduction

The International Lipid-based Nutrient Supplements (iLiNS) Project is a multi-country (Ghana, United States, Finland, France, Malawi and Burkina Faso) research collaboration with the goal to expand the evidence base for the use of lipid-based nutrient supplements (LNS) for preventing malnutrition in vulnerable populations. In Ghana the iLiNS Project focuses on the efficacy of LNS for pregnant and lactating women and their infants, and is referred to as iLiNS DYAD-G. Primary data collection began in December 2009. Below we describe the iLiNS DYAD-G's statistical analysis plan whilst data collection is still ongoing, before any knowledge of the study results. Data collection is expected to be completed by end of 2013.

2.0 Overview of study

2.1 Title

The iLiNS DYAD-G study is a randomized, partially double blind, controlled trial that compares three micronutrient treatments, and targets women during pregnancy (from ≤ 20 gestational weeks to delivery) and the first six months postpartum, and their offspring during infancy (from birth to 18 mo of age). The treatments are: (a) Daily iron and folic acid during pregnancy, and calcium (Ca) only (akin to a placebo) during the first 6 months postpartum, with no supplementation for offspring during infancy; (b) Daily multiple micronutrients (1-2 RDA of 18 vitamins and minerals) during pregnancy and the first 6 months postpartum, with no supplementation for offspring during infancy, and (c) Daily LNS during pregnancy and the first 6 months postpartum (LNS-P&L with similar vitamin and mineral content as the daily multiple micronutrients, plus Ca, P, K, Mg and essential fatty acids), with LNS for offspring (LNS-20gM with 22 vitamins and minerals with concentrations based on RNIs for infants) during infancy.

2.2 Study population

We screened (by means of a questionnaire) pregnant women attending usual ante-natal clinics who were at least 18 years of age and were no more than 20 weeks pregnant (based on either fundal height measurement or ultrasound), and excluded those who refused the screening, or were more than 20 weeks pregnant or less than 18 years of age. Women who passed the screening and later gave consent to participate in the study were considered recruited, but not yet enrolled. Recruited women who attended baseline laboratory and anthropometric assessments, and were randomized into one of the three treatment study groups were considered enrolled. Only enrolled women were considered full participants of the study.

In terms of pregnant women's ages, there was no upper limit for inclusion into the study, and in terms of gestational age, there was no lower limit. All singleton offspring of the pregnant women became part of the study, but when a woman gave birth to more than one infant, only one was randomly selected for inclusion in the study.

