2.3 Inclusion criteria

2.3.1 Inclusion criteria (pregnant women)

Pregnant women were eligible for inclusion in the study if all of the following criteria were met:

a) At least 18 years of age

- b) No more than 20 wk of gestation (as determined by fundal height measurement or ultrasound scan) at the time of enrolment.
- c) Prepared to sign an informed consent
- d) Participated in baseline anthropometric and laboratory assessment.

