2.4.2 Exclusion criteria (offspring)

An infant was excluded from the study if the infant's mother had multiple births (more than one child from the pregnancy) and the infant was not randomly selected for inclusion into the study.

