2.9 Analysis principles

- The primary analysis will be by intention-to-treat. That is, results for all women enrolled (including data on their infants) will be analyzed according to the group to which they were assigned regardless of any protocol violations. Data on subjects who were lost to follow-up because of death, travel from the study site, or refusal to continue with the study will be included in the analysis if available.
- All tests will be two-sided, at 5% level of significance.
- Where more than 10% of observations are missing for a dependent variable, we will report the number of observations used in the analysis.

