4.8 Analysis of the effect of the intervention

The analysis of the effect of the intervention (at single time points or repeated measures) will begin with testing the null hypothesis of no difference among the three treatment groups using ANCOVA or logistic regression, and controlling for pre-specified covariates including, in the case of women, baseline values. Because infants will not have true baseline values unaffected by intervention, most of the covariates used in analyses involving infants will be mothers' baseline characteristics. Only covariates significantly associated with an outcome at 10% level of significance in a bivariate analysis will be include in the final adjusted analysis. This means we may have different sets of covariates for each outcome.

For all analyses, if the global null hypothesis is rejected at 0.05 level, then we will perform post-hoc pairwise comparisons of all three groups using Tukey-Kramer adjustment (for continuous variables) or the "Contrast" statements (for categorical variables) in SAS. We will also use Scheffe's test to assess whether the LNS group differs from the non-LNS groups with respect to most outcomes, and whether the IFA group differs from the non-IFA groups with respect to iron outcomes or variables such as morbidity which might be affected by iron status.

The effects of potential effect modifiers will be assessed with an interaction term in the ANCOVA or logistic regression model. Significant interactions (p < 0.05) will be further examined with stratified analyses, estimation of separate regression lines, or estimation of adjusted means at key points of the covariate, in order to understand the nature of the effect modification.

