4.9 Comparison of primary outcomes at birth and 18 months of age

The ANCOVA to determine the effects of the intervention on birth length (crude length and length-for-age z-score) and length-for-age z-score at 18 mo among the three intervention groups will be performed using PROC GLM. Results will be summarized as mean and SD and tabulated, by group (**Table 2** and **Table 3**).

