4.10 Comparison of secondary outcomes

i. Comparison at single time points

Comparison of secondary outcomes at single time points will be performed using PROC GLM (for continuous outcome variables), and PROC FREQ and PROC LOGISTIC for categorical outcome variables. Continuous variables will be summarized using either mean and SD, or median and range. Categorical variables will be summarized using percentages and Odds Ratios, with 95% Confidence Intervals (95% CI).

Analysis of several secondary outcomes at birth and 18 months of age will be presented alongside the primary outcomes in **Table 2** and **Table 3** as well as in **Table 4**. Prior to the analysis of additional secondary outcomes at other single time points, this SAP will be updated to include those specific single time points, and how results will be presented.

ii. Comparison of repeated measures

For continuous outcome variables, a linear mixed model (PROC MIXED) will be used to compare patterns in the outcome variables across time among the groups. For categorical variables, a variant mixed model logistic regression (SAS PROC GLIMMIX) will be used. Prior to analysis of repeated measures, this SAP will be updated to include the specific analyses and the presentation of the results.

4.11 Selection of covariates and effect modifiers in the analysis of primary outcomesBelow we list the two primary outcomes to be analyzed (both at single time points), and indicate the covariates and effect modifiers that will be used for each analysis. Each of the effect modifiers will be considered separately in the regression model to avoid collinearity.

Primary	Analysis	Covariates	Effect modifiers
outcome			
variable			
Birth length	ANCOVA	- Maternal height	- Maternal height
(crude	(SAS Proc	- Maternal BMI	- Maternal BMI
length in cm	glm)	- Gestational age at enrolment	- Gestational age at enrollment
and length-		- Maternal age	- Maternal age
for-age z-		- Child sex	- Child sex
score)		- Maternal education	- Maternal education
		- Proxy for SES	- Proxy for SES
		- Parity	- Parity
		- Season at enrolment	- Season at enrolment
		- Mother's marital status	- Maternal anemia at enrollment
Length-for-	ANCOVA	- Maternal height	- Maternal height
age z-score	(SAS Proc	- Maternal BMI	- Maternal BMI
at 18 months	glm)	- Gestational age at enrolment	- Gestational age at enrollment
		- Maternal age	- Maternal age
		- Child sex	- Child sex
		- Maternal education	- Maternal education
		- Proxy for SES	- Proxy for SES

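### Infants from multiple births enter the primary analyses, but section 4.11 lists no multiple-pregnancy covariate, which gives up a modest amount of precision

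*SAP*

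**What the plan says.** Section 2.2 of the SAP deals with multiple births by selection: "when a woman gave birth to more than one infant, only one was randomly selected for inclusion in the study". Section 2.4.2 matches it. An infant is excluded only where "the infant's mother had multiple births (more than one child from the pregnancy) and the infant was not randomly selected", so the multiple pregnancy itself stays in the trial. Section 2.9 brings the selected infant into the primary analysis, because "results for all women enrolled (including data on their infants) will be analyzed according to the group to which they were assigned".

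The primary analysis in 4.9 is a three-group ANCOVA. Section 4.11 undertakes to "indicate the covariates and effect modifiers that will be used for each analysis". For both primary outcomes the covariates are maternal height, BMI, gestational age at enrolment, maternal age, child sex, maternal education, an SES proxy, parity, season at enrolment and marital status. Multiple pregnancy is not among them, nor among the effect modifiers in 4.6 and 4.11. Section 4.8 then narrows the list: "Only covariates significantly associated with an outcome at 10% level of significance in a bivariate analysis" go into the final adjusted model. No singleton-only analysis is planned.

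**The concern.** The plan recognises multiple births and writes a selection rule for them, but leaves them out of the model. If infants from multiple pregnancies tend to be shorter at birth, that difference goes into the error term. No listed covariate stands in for it: gestational age at delivery, the nearest candidate, is a secondary outcome in 2.7.2.

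What is at stake is some precision for the primary birth-length comparison and some protection against a chance excess of multiples in one arm. There is also a question of timing. Section 1.0 says the plan was written before any results were known. A multiple-pregnancy term or a singleton restriction added then is clean. Either one brought in after unblinding would be a post-hoc choice on a primary outcome.

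**Working it through.** **1. Is multiple pregnancy really outside the model?** Sections 2.2, 2.4.2 and 2.9 put the selected infant in the analysis. Section 4.11 gives a closed list without plurality. The screen in 4.8 works on pre-specified covariates, so it can remove a term but cannot add one. The omission is confirmed.

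**2. Is adjustment legitimate?** Section 2.3.1 requires "No more than 20 wk of gestation (as determined by fundal height measurement or ultrasound scan) at the time of enrolment", so women are randomised while already pregnant, and the number of fetuses conceived precedes assignment. Plurality at birth must be known in order to apply 2.4.2. Child sex, also set at conception and seen at birth, is already listed. One qualification applies: loss of one fetus after randomisation could change the status recorded at delivery.

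**3. The plan's own sample size.** Section 3.1 uses an effect size of 0.3, three groups, 80% power and alpha 0.05. Take a one-way ANOVA F test with the two extreme groups 0.3 SD apart and the third midway:

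- f² = 0.3² / 6 = 0.015
- smallest n with power of at least 80%: 216 per group (power 0.8017)
- 3 × 216 = 648, and 648 / 0.75 = 864

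All three stated figures are reproduced.

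**4. Size of the omission.** The SAP gives neither input below, so both are assumptions: p, the share of pregnancies that are multiple, 1.5% to 4%; and D, the birth-length deficit in within-group SD, 1.0 to 1.5.

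- Share of variance explained = p(1−p)D² / (1 + p(1−p)D²)
- Power with the term: the same F test with f² = 0.015 / (1 − share) and one error df fewer
- SD of the chance shift in a pairwise difference = √(2p(1−p)D² / 216)

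| p | D | p(1−p)D² | Variance share | Power at 216 per group | SD of chance shift |
|---|---|---|---|---|---|
| 1.5% | 1.0 | 0.0148 | 1.5% | 80.8% | 0.012 |
| 1.5% | 1.5 | 0.0332 | 3.2% | 81.5% | 0.018 |
| 4% | 1.0 | 0.0384 | 3.7% | 81.7% | 0.019 |
| 4% | 1.5 | 0.0864 | 8.0% | 83.5% | 0.028 |

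The gain over 80.2% is about 0.6 to 3.4 percentage points. The number of such infants among 648 analysed would be 648 × 0.015 ≈ 10 to 648 × 0.04 ≈ 26.

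**5. The chance shift in proportion.** The ordinary standard error of a pairwise difference is √(2/216) = 0.096 within-group SD. Leaving multiple pregnancy out multiplies it by √(1 + p(1−p)D²), that is by 1.007 to 1.042. Birth length is measured within 48 hours of delivery, when losses should be below the 25% allowed by 18 months. With 288 per arm (864 / 3) the SD of the chance shift would be 0.010 to 0.024.

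**6. Would the 10% screen have kept the term?** With 648 infants the expected z is D√(648·p(1−p)), which is 3.1 at the low end and 7.5 at the high end, against a two-sided 10% cut-off of 1.645. On these assumptions it would very probably have been retained had it been listed.

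**The case against.** Leaving out a prognostic covariate does not make a randomised ANCOVA invalid, and which factors to list is partly judgement. That stands, and it limits the point to precision.

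A reader might infer four stronger things, none of which the document supports:

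- **That the comparison is biased.** Randomisation makes it unbiased. Random imbalance in multiples is already reflected in the residual variance and the confidence interval.
- **That the trial is underpowered.** Section 3.1 defines the effect relative to the pooled SD, which over all analysed infants already includes variation from multiples. It takes no credit for covariates, so the term would add power above plan and repairs no shortfall.
- **That the Table 2 secondary outcomes, such as birth weight, gestational age at delivery and prematurity, are wrongly adjusted.** Section 4.12 leaves secondary covariates to a later update, so nothing has yet been omitted there.
- **That multiple birth as recorded is strictly a pre-randomisation variable.** Plurality at conception is; plurality at delivery could be changed by a fetal loss in between.

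It is also fair to object that the rate and the deficit are assumed throughout, that the 8% figure needs both upper assumptions together, and that nothing shows the deficit persisting to 18 months. All of this stands. What remains is a real omission in the section that fixes the primary covariates, and it costs little to correct.

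**Conclusion.** The point holds as a minor one. One infant per multiple pregnancy is in the primary analyses and no term accounts for it, so its effect on birth length stays in the residual variance. With 1.5% to 4% multiple pregnancies and a deficit of 1.0 to 1.5 within-group SD, neither of which comes from the SAP, the unexplained share is about 1.5% to 8% of birth-length variance. A chance imbalance between two arms of 216 would typically shift a difference by 0.01 to 0.03 SD, against a target of 0.3 SD. For LAZ at 18 months the gain is not quantified and may be smaller.

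**What to change.** In section 4.11, add multiple pregnancy (yes/no) as a covariate for birth length (cm and LAZ) and for LAZ at 18 months. State there and in 4.8 that this term is kept regardless of the 10% bivariate screen; otherwise the two sections would conflict. Define it from plurality known at enrolment where available, and otherwise from plurality at delivery. Add one sensitivity analysis of birth length restricted to singletons. Leave the secondary birth outcomes in Table 2 to the update promised in 4.12, where the same term can be considered.

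The cost is SAP wording, one degree of freedom and one extra model run. Plurality at delivery is already needed to apply 2.4.2, so no new data collection is required. The remaining downside is a small risk that, where plurality is known only at delivery, loss of one fetus after randomisation has changed the recorded status.

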2.3 Inclusion criteria

2.3.1 Inclusion criteria (pregnant women)

Pregnant women were eligible for inclusion in the study if all of the following criteria were met:

a) At least 18 years of age

- b) No more than 20 wk of gestation (as determined by fundal height measurement or ultrasound scan) at the time of enrolment.
- c) Prepared to sign an informed consent
- d) Participated in baseline anthropometric and laboratory assessment.

2.3.1 Inclusion criteria (infants)

Infants were eligible for the study if they were delivered from the pregnancy for which their mothers were enrolled into the study.

2.4 Exclusion criteria

2.4.1 Exclusion criteria (pregnant women)

Pregnant women were excluded from the study if one or more of the following criteria were present:

- a) HIV positive (as from the Ante-natal card).
- b) Known to be allergic to milk or peanut.
- c) Presence of asthma, epilepsy, tuberculosis or any other chronic disease (e.g. malignancy) requiring frequent medical attention (as from the Ante-natal card).
- d) Not residing in the study site (defined by the area between the southern end of Somanya and the northern end of Kpong, along the Somanya-Kpong trunk road in the Manya Krobo and Yilo Krobo districts).
- e) Intention to move from the study site.
- f) Unwilling to receive into the home the study's field workers who would deliver study supplements and administer questionnaires.
- g) Already participating in a clinical trial.
- h) Unwilling to take study supplement.

2.4.2 Exclusion criteria (offspring)

An infant was excluded from the study if the infant's mother had multiple births (more than one child from the pregnancy) and the infant was not randomly selected for inclusion into the study.

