2.8.2 Serious adverse events

Serious adverse events (SAE) outcomes:

- a) Number of SAEs reported, ie. if a subject has more than one occurrence of SAEs, all the SAEs will be counted.
- b) Number and proportion of subjects with SAEs i.e. if a subject has more than one occurrence of SAEs, the subject will be counted only once.

Conditions regarded as SAEs were:

- a. Death of subject.
- b. Any loss of pregnancy regardless of gestational age.
- c. Hospitalization (overnight stay in the hospital because of illness).
- d. Hemoglobin less than 5.0 g/dl (or 50 g/l).
- e. Subject extremely ill. This is used to define (a) "life-threatening conditions" (including seizures, coma, tetany, diabetic ketoacidosis, disseminated intravascular coagulation, diffuse petechiae, paralysis, acute psychosis, severe depression), (b) "persistent or significant disability / incapacity" and (c) "other serious medical condition".
- f. Congenital abnormality/ birth defect.

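### The death of a liveborn, non-selected twin has no place in the SAE outcomes, because that infant is excluded from the study and SAEs are counted by subject

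*SAP*

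**What the plan says.** Two sections of the SAP set the status of twins. Section 2.2 states that "when a woman gave birth to more than one infant, only one was randomly selected for inclusion in the study". Section 2.4.2 puts the same rule as an exclusion from the study, applied where "the infant's mother had multiple births (more than one child from the pregnancy) and the infant was not randomly selected". Both speak of the study as a whole. Neither limits the rule to growth or to any other outcome.

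Section 2.8.2 then defines two SAE outcomes. The first is "Number of SAEs reported, ie. if a subject has more than one occurrence of SAEs, all the SAEs will be counted". The second is "Number and proportion of subjects with SAEs", each subject counted once. Its list of conditions opens with "Death of subject". It also includes loss of a pregnancy at any gestational age and "Congenital abnormality/ birth defect", and neither of those two items names a subject.

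On exposure, section 2.1 says that the trial "targets women during pregnancy (from ≤ 20 gestational weeks to delivery) and the first six months postpartum". Section 2.9 says that enrolled women, with the data on their infants, are analysed by assigned group. It does not mention the twin rule.

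**The concern.** Taking one infant per pregnancy is sound for the growth analysis, because it keeps the observations independent. A count of harms does not need that restriction. The infant left out had the same exposure before birth as the infant kept in, and the SAP gives no safety reason for separating them.

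At stake is whether the tabulated deaths cover all liveborn infants exposed through the enrolled pregnancies. Under the rules as written they do not. Two analysts who filled the gap differently could also report different mortality counts from the same data.

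**Working it through.** The point rests on reading the sections together. The arithmetic only gives a sense of scale.

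**Step 1: who is a subject.** Section 2.3 (infant inclusion criteria) makes any infant of the enrolled pregnancy eligible. Section 2.4.2 then removes the infant not drawn, and removes it from the study. That infant is therefore not a subject for any purpose, safety included.

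**Step 2: what each SAE item requires.**

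| Item in 2.8.2 | Tied to a subject? | Event in a non-selected co-twin |
|---|---|---|
| Death | Yes, in the item itself | Not counted after live birth |
| Loss of pregnancy | No; attaches to the enrolled woman | Could be recorded under the mother; unclear if only one twin is lost |
| Congenital abnormality | No | Could be recorded under the mother; not settled |

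The mother remains a subject whatever happens to her infants, so the last two rows have a possible route into the counts. The first row has none, because the infant who died is not a subject.

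**Step 3: does section 2.9 repair this?** It brings in data on the infants of enrolled women, but it is a general statement about analysis by assigned group. It does not override an explicit exclusion from the study.

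**Step 4: base for the scale.** Section 3.1 gives 3 × 216 = 648 and, with 25% loss, 648 / (1 − 0.25) = 864 women. Section 3.3 agrees: 96 × 9 = 864 envelopes. Equal allocation gives 864 / 3 = 288 per group.

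**Step 5: scale, by assumption.** The SAP gives neither a multiple-birth rate nor an infant mortality rate. Assume that 1% to 4% of pregnancies are twin pregnancies, that each leaves out one infant, and that no pregnancies are lost before birth.

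- Co-twins left out: 864 × 0.01 = 8.6, to 864 × 0.04 = 34.6, so about 9 to 35.
- Per group: 8.64 / 3 = 2.9, to 34.56 / 3 = 11.5, so about 3 to 12.
- Deaths, at an assumed co-twin mortality of 2% to 15%: 8.64 × 0.02 = 0.17, to 34.56 × 0.15 = 5.2, so about 0.2 to 5 over all three groups.

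**The case against.** The strongest reply is that the SAP nowhere says co-twin events are to be left out of the safety tables. How an SAE is attributed between mother and infant, and how events in offspring outside the study are reported, is commonly set in a protocol, and none is at hand. This has weight, but it does not remove the point. The SAP itself states both the exclusion and the subject-based SAE outcomes. Even if a protocol rule captured the death, the outcomes defined here would still give it no place.

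A second reply is that the exclusion is written in the past tense and has already been applied, so new wording cannot bring infants back into follow-up. That stands, and it limits the remedy to events already known. The SAP does not show that co-twin data were collected, and it does not mention a delivery record as a source.

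Three stronger readings are tempting, and the document supports none of them:

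- *Birth defects and stillbirths in co-twins are lost as well.* Section 2.8.2 does not tie those items to a subject, so they may be recorded under the mother. The fault there is ambiguity, including where only one twin is lost.
- *The data and safety monitoring board would see an undercount.* Section 3.5 lets the board request all-cause mortality by treatment group. It does not restrict that request to selected infants or to the 2.8.2 definitions.
- *The comparison between arms is biased.* The draw is random and the same rule applies in every arm, so no bias is shown.

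**Conclusion.** The concern holds for one event: the death of a liveborn infant of a multiple birth who was not drawn. Under 2.2, 2.4.2 and 2.8.2 as written, that death is uncounted although the infant was exposed in utero. The SAE outcome is therefore incomplete by a stated rule, which is more than silence on a detail. For birth defects and pregnancy loss the sections need clarifying, but the text does not compel their omission.

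The size is small and unknown. The range in the working rests wholly on assumed twin and mortality rates, and its lower end is close to no deaths at all. The case for acting is that each such event is a death in an exposed infant and that the correction is cheap. The primary outcomes and the sample size are not affected.

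**What to change.** In 2.4.2, state that the one-infant rule applies to the growth, biochemical and developmental outcomes.

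In 2.8.2, state that stillbirth, infant death and congenital abnormality are counted for every infant of the enrolled pregnancy, selected or not, by the mother's assigned group. Report them in two ways: per woman (any such event) and per infant. Limit the non-selected infants to events known from existing contacts with the mother. Section 4.7 already has her visited every two weeks until six months postpartum, and the selected infant weekly until 18 months.

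The cost is a few sentences in the SAP and two extra lines in a safety table. No efficacy analysis changes. There are two downsides. Per-infant counts will include correlated twins, which the per-woman count handles. Ascertainment of non-selected twins may also be less complete than for followed infants, and a note to the table should say so.
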